Specific Aim 1: To determine the impact of cocaine dependence and oxytocin on functional connectivity between corticolimbic brain regions during acute social stress. Psychophysiological interaction (PPI) analysis using the amygdala as the seed region will be used to assess significant task (stress condition > control condition) x seed interactions. Subjective anxiety and craving data will be collected at baseline and after each run of the MIST.

Hypothesis 1A: The HC-PBO group will exhibit greater functional connectivity between the amygdala and prefrontal cortical regions (orbitofrontal and anterior cingulate cortices) than the CD-PBO group.

Hypothesis 1B: The CD-OT group will exhibit greater functional connectivity between the amygdala and prefrontal cortical regions (orbitofrontal and anterior cingulate cortices) than the CD-PBO group.

Hypothesis 1C: The CD-OT group will report lower subjective anxiety and craving than the CD-PBO group.

Specific Aim 2: Use an implicit facial affect recognition paradigm to determine the impact of cocaine dependence and oxytocin on amygdala activity in response to fearful faces. The BOLD signal measured during neutral faces will be subtracted from the BOLD signal measured during fearful faces.

Hypothesis 2A: The CD-PBO group will exhibit greater amygdala activity in response to fearful faces than HC-PBO group.

Hypothesis 2B: Compared with the CD-PBO group, participants in the CD-OT group will exhibit lower amygdala activity in response to fearful faces.

Currently there are no FDA approved medications for the treatment of cocaine dependence. Identifying the neurobiologic substrates of emotion-related behavior in cocaine-dependent individuals may help in the identification of targets for the development of treatment strategies aimed at controlling emotion-related behavior.

RESEARCH STRATEGY

A. SIGNIFICANCE

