The amygdala response to emotional faces that are presented outside the focus of attention (i.e. implicit tasks) is significantly greater than that observed during overt (explicit) presentation of the same stimuli (Critchley et al., 2000). Emotional adult faces will be selected from a variety of sources are standardized in size and enclosed in the same oval surround (Ekman, 1976). [name] (Co-I) has developed a corpus of faces for a recent project (National Institute of Mental Health, R21 MH086958-01, “A comparative developmental connectivity study of face processing”) that will be used for the present project. The faces will depict male and female Caucasian, Asian and African Americans expressing three different categories of emotion; fear, anger, and happiness. Neutral faces will also be presented (Figure 5). Because the participants will also be from different ethnic categories, it is important to include a mixture of races. In a block design, participants will view a series of faces (for 27.5 sec) within a block and report on the gender of those faces at the end of the block (for 5 sec). Each block will present 56 faces that depict the same emotion and same gender so there will be 6 pseudorandomly ordered task blocks (3 emotions x 2 genders) and 7 rest blocks (27.5 sec each) that present a crosshair to be fixated. In each task block, each emotional face will be presented for 33 msec. followed by a neutral face mask (from a different individual) for 167 msec. followed by a blank screen for 291 msec. At the end of the block participants will report the gender using two buttons on a response pad. Assignment of face sets to sessions will be counterbalanced across subjects.

Payment to Participants

Subjects will be paid with Greenphire debit cards or cash for each completed study visit as follows: \$75 for completing baseline assessments to see if you meet study requirements (\$25 for the physical exam and \$50 for the interview) and \$150 for completing the scanning session. The total amount that they may receive for participating in the study if they complete all study visits is a maximum of \$225. If subjects choose not to complete the study, they will be compensated for the part(s) they have completed. Subjects who come to their

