Data Analysis: Following preprocessing (described above), within-task data from individual participants will be analyzed with a fixed-effects general linear model (GLM), with each emotion (described below) modeled as a box-car function convolved with a double-gamma hemodynamic response function. The response period at the end of each block will also be modeled as a separate variable to remove effects of explicit decision making and response selection. The GLM procedure is repeated for each voxel with six movement parameters (3 rotation values in radian and 3 translation values in millimeter) included as covariates to control for the influence of head motion on the data. Following first-level analysis, subject-specific contrasts will be entered into second-level, random-effects analyses. Since the hypotheses associated with Specific Aim 2 explore amygdala activity, we will use a region of interest approach (ROI). The BOLD signal from the left amygdala will be extracted using an anatomical mask generated by a 12-mm diameter sphere located in the center of the left amygdala using the MNI coordinates (x, y, z = -22, 0, -22). The percent signal change between the fearful and neutral conditions (contrast of interest) will be calculated for each participant. Separate random-effects one-way analysis of variance tests (ANOVA) will be used to test for the following group differences (Hypothesis 2A: CD-PBO vs. HC-PBO) and (Hypothesis 2B: CD-PBO vs. CD-OT). Since human neuroimaging studies have found that other brain regions play a role in implicit emotional processing, including the right amygdala and insula (Davidson et al., 1999; Shi et al., 2013), secondary analyses will also include these regions. In addition, OT may impact amygdala responding to happy faces (Domes, Heinrichs, Glascher, et al., 2007), therefore group differences in amygdala responding in the happy-neutral contrast may be explored in future analyses. For multiple comparisons that are not part of the hypothesis a priori, the Bonferroni correction will be used. In addition, contrasts of other pertinent baseline characteristics will be performed between groups. If the groups differ significantly on any of these baseline characteristics, the corresponding variables will be used as covariates in the above analyses. The statistical analyses will be conducted using SAS 9.3 software (SAS Institute Inc., Cary, NC, USA).

Power and Sample Size

Specific Aim 1

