1. RISKS TO THE SUBJECTS

1.1 Human Subject Involvement and Characteristics

Admission into the study is open to men and women and to all racial and ethnic groups, aged 18-65. We will scan 160 study participants including (1) cocaine-dependent (CD) individuals (n=80) and (2) healthy control (HC) subjects free of major Axis I diagnoses (n=80). Inclusion/exclusion criteria are listed below:

General Inclusion/Exclusion Criteria

Inclusion Criteria

1. Age 18-65.
2. Subjects must be able to provide informed consent and function at an intellectual level sufficient to allow accurate completion of all assessment instruments.
3. Subjects must consent to remain abstinent from all drugs of abuse (except nicotine) for the three-day period immediately prior to the study visit.
4. Subjects must consent to random assignment.
5. Subjects must have a negative breathalyzer, urine drug screen at the study visit.
6. Subjects must consent to the study visit which includes an outpatient visit to the ASD and completing one functional magnetic resonance imaging (fMRI) scanning session.

Exclusion Criteria

1. Subjects with evidence of or a history of significant hematological, endocrine, cardiovascular, pulmonary, renal, gastrointestinal, or neurological disease including diabetes.
2. Subjects with a history of or current psychotic disorder or bipolar affective disorder.
3. Subjects with current major depressive disorder or post-traumatic stress disorder.
4. Subjects taking any psychotropic medications, including SSRI's or other antidepressants, opiates or opiate antagonists. Subjects taking trazodone or non-benzodiazepene hypnotics for sleep will be included.
5. Women who are pregnant, nursing or of childbearing potential and not practicing an effective means of birth control.
6. Subjects who have a BMI that would preclude them from fitting comfortably in the scanner.
7. Persons with ferrous metal implants or pacemaker.
8. Subjects that are claustrophobic.
9. Subjects with significant psychiatric or medical problems that would impair participation or limit ability to complete the scanning session.
10. Subjects that require maintenance or acute treatment with any psychoactive medication including anti-seizure medications which could potentially interfere with fMRI data acquisition.

Group – Specific Inclusion/Exclusion Criteria

Individuals with Cocaine Dependence

Inclusion Criteria

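### Aim 2 is defined as fearful minus neutral faces, but the face-task schedule contains no neutral block

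*Combined protocol and SAP*

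**What the plan says.** Three places in the protocol bear on this.

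- **Specific Aims, Specific Aim 2**, defines the measure: "The BOLD signal measured during neutral faces will be subtracted from the BOLD signal measured during fearful faces".
- **C3f Statistical Methods, Specific Aim 2, Data Analysis**, repeats it for Hypotheses 2A and 2B: "The percent signal change between the fearful and neutral conditions (contrast of interest) will be calculated for each participant". The same paragraph mentions a happy-minus-neutral contrast for later work.
- **Implicit Facial Affect Recognition Task** describes what is shown. The faces cover "three different categories of emotion; fear, anger, and happiness. Neutral faces will also be presented (Figure 5"). On block content: "Each block will present 56 faces that depict the same emotion and same gender". On the schedule: "there will be 6 pseudorandomly ordered task blocks (3 emotions x 2 genders) and 7 rest blocks". The rest blocks show a fixation cross. Within a task block, "each emotional face will be presented for 33 msec. followed by a neutral face mask"; the face lasts 33 ms, the mask 167 ms and the blank that follows 291 ms. Each block has 27.5 s of faces and a 5 s response period.

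Section 5.1, Summary of the Protocol, lists the amygdala signal to implicit fearful faces as the third primary outcome.

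**The concern.** The analysis subtracts a condition that the schedule does not contain. Three emotions by two genders use up all six task blocks, and rest blocks show no faces. The task section says that neutral faces are also shown but gives them no block, number or timing.

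If the block list is simply miscounted, only the text is wrong. If the task was built to the written list, the specified analysis of 2A and 2B cannot be done. What would remain is fear against fixation, which mixes fear with the general response to seeing faces, or fear against another emotion. Were this noticed only at analysis, the replacement for a primary outcome would be chosen with the data in hand.

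**Working it through.** **Inputs** (Implicit Facial Affect Recognition Task): 3 emotions, 2 genders, 56 faces per block, 33 + 167 + 291 ms per trial, 27.5 s of faces and 5 s of response per task block, 7 rest blocks of 27.5 s. The model is from C3f, Aim 2: a box-car per emotion convolved with a double-gamma response function, plus a response-period regressor. The documents give two repetition times: 2.5 s (MRI Data Acquisition) and 2.2 s (Preprocessing).

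**1. The plan's own figures reproduce.**
- Task blocks: 3 × 2 = 6. Six task blocks separated and flanked by rest give 7 rest blocks.
- Block length: 56 × (33 + 167 + 291) ms = 56 × 491 ms = 27.496 s, against 27.5 s stated.

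The written schedule is therefore consistent in itself as a three-emotion design.

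**2. Where could neutral faces be?**
- *In blocks of their own:* 6 blocks − (2 fear + 2 anger + 2 happiness) = 0. Of 6 × 27.5 = 165 s of face time, 0 s has neutral targets.
- *Mixed into the listed blocks:* ruled out by the one-emotion rule. The time left per block is 27.5 − 27.496 = 0.004 s.
- *As the masks:* 6 × 56 = 336 masks, or 336 × 0.167 = 56.1 s. Per emotion this is 112 × 0.167 = 18.7 s. Every mask follows an emotional face.
- *As the rest blocks:* these show a cross, not faces.

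**3. Is the contrast estimable?** Take a design matrix with columns for fear, anger, happiness, neutral, response period and a constant.
- With no neutral block, the neutral column is all zeros: 6 columns, rank 5.
- With the masks as neutral, the mask is on in exactly the task blocks, so neutral = fear + anger + happiness (computed difference 0): 6 columns, rank 5.

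In both cases fear minus neutral is not estimable. The identity holds for any block order and either repetition time. Adding the six movement covariates cannot remove a linear dependence. Without the neutral column the rank is 5 of 5, and fear minus fixation, fear minus anger and fear minus happy are all estimable.

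**4. With neutral as a fourth category** (an assumption; the documents do not say this), 4 × 2 = 8 task blocks and, with rest still interleaved, 9 rest blocks. The design has rank 6 of 6 and fear minus neutral is estimable.
- Run as written: 6 × 32.5 + 7 × 27.5 = 387.5 s.
- Run with neutral: 8 × 32.5 + 9 × 27.5 = 507.5 s, which is 120 s longer.

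**5. Does the stated volume count settle it?** Preprocessing gives 271 volumes at 2.2 s: 271 × 2.2 = 596.2 s. This matches neither 387.5 nor 507.5 s, so it does not show which design was meant.

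**The case against.** The strongest reply is that this is a slip in one parenthesis. The aims and the analysis section both treat neutral as a condition, and the task section says neutral faces are shown and points to Figure 5, which is not available here. A careful reader would query the count, and correcting it costs one sentence. That reading is plausible and may be the likelier one. It does not remove the contradiction: the text nowhere gives a neutral block, and if Figure 5 shows one, it conflicts with the count of six.

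Other objections have some force.

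- *The rank result restates that no neutral block is listed, and nobody proposed a mask regressor.* Largely true. Its use is to close off the one way the listed stimuli might have supplied a neutral condition.
- *The line "Assignment of face sets to sessions will be counterbalanced across subjects", set against "completing one functional magnetic resonance imaging (fMRI) scanning session", need not mean that the text came from another study.* Agreed; it is a weak hint, and the conclusion does not rest on it.
- *The extra 120 s may not lengthen the acquisition, given 596.2 s of volumes.* Fair. The figure is a difference between two computed task lengths.
- *Much of the remedy is conditional.* True. It applies only if neutral blocks were not run, which the documents do not show.
- *Hypotheses 2A and 2B do not themselves claim fear specificity.* True of their wording, but Aim 2 defines the measure by subtraction. A change to fixation would change what is measured and should be stated.

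**Conclusion.** The concern holds. The protocol contradicts itself on whether neutral-face blocks exist, and a task built exactly to the written schedule cannot yield the contrast specified for a primary outcome. The size is absolute on that reading: 0 of 6 task blocks, 0 of 165 s, and no sample size helps. Confidence is high for the contradiction only. Whether the task as run lacks neutral blocks cannot be told from the documents. The run lengths assume that rest stays interleaved in the stated 6 + 7 pattern. The point needs correction in either case, since the text alone cannot show which version is true.

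**What to change.** 1. **Check the block list in the stimulus script actually used.**
2. **If neutral blocks are run**, correct the task section to the true list, for example 4 categories × 2 genders = 8 task blocks with 9 rest blocks (507.5 s). Cost: one sentence.
3. **If they are not run**, add one neutral-target block per gender for the remaining scans. One option is to add two rest blocks as well (+120 s of task time). The other is to let the neutral blocks replace the anger blocks, which no stated contrast uses (387.5 s, with loss of the anger data). Both give two fear and two neutral blocks, 55 s each; the choice is the investigators'. Cost: a script change and protocol text.
4. **For participants already scanned without neutral blocks**, specify a contrast that the data contain before any face-task group results are examined, by cocaine status or by treatment. Waiting for the treatment unblinding is not enough: the blind described under Medication Administration covers oxytocin and placebo, not cocaine status. Fear minus fixation is the main candidate, with 2A and 2B reworded to say that it is not specific to fear. Fear minus happy or fear minus anger would remove the shared face and mask response. However, the Significance section reports that fearful and happy cues both raise amygdala activity and that oxytocin dampens responses to aversive and positive cues, so a true difference could partly cancel. If either is used, state that limit.
5. **Do not pool fear minus neutral across task versions.** Analyse it only in scans with neutral blocks. Fear minus fixation may use all participants with task version in the model. This matters most for 2A: the cocaine and control groups are recruited, with monthly tailoring (C3b), so their mix of versions could differ.

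If scanning began without neutral blocks, fear minus neutral will have fewer than the planned 40 per group; the number already scanned is not given.

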The study will use a block design of three, six-minute runs separated by two-minutes of rest for feedback, for a total of 24-minutes. During each run, participants will be exposed to 40-second blocks of three different conditions (rest, control, and stress). Prior to the task, a research assistant will meet with each participant and described the parameters of the task. The participants will be shown images of what the screen will look like during each condition. The participants will be instructed to relax during the rest condition and focus on the screen. During the control condition, the participants will be asked to answer math problems as accurately as possible but will also be told that their responses will not be recorded. During the stress condition, the participants will be asked to perform the math task as quickly and accurately as possible. They will be given immediate feedback about their performance and will be able to see the performance level of an “average” person through a performance bar that will be located at the top of the screen. A strict time limit will be enforced throughout the stress condition. The participants will be told that the average person would answer about 85% of the questions correctly, while in reality, the program’s algorithm limits the participants’ performance rate to between 35-45%. At the end of runs one and two, the participants will be given negative feedback from the investigator and will be urged to improve their performance so that their data may be included in the study. To minimize the effects of scanner drift, the beginning condition will be counterbalanced between participants. However, the sequence of conditions will be constant (i.e. control condition will follow the rest condition and the stress condition will follow the control condition).

Implicit Facial Affect Recognition Task

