scheduled study visit and provide a clean urine drug screen the first time they're scheduled, they will draw 7 chips from a bowl containing 250 chips that are assigned a certain value. Most chips are worth \$1.00, some are worth \$10.00, one chip is worth \$50.00 and one chip is worth \$100.00. If their visit has to be re-scheduled for any reason, they will be allowed to draw 3 chips.

Payments that subjects receive from MUSC for participating in a research study are considered taxable income per IRS regulations. Payment types may include, but are not limited to: checks, cash, gift certificates/cards, personal property, and other items of value. If the total amount of payment subjects receive from MUSC reaches or exceeds \$600.00 in a calendar year, they will be issued a Form 1099. Participants will complete a W-9, either in person or via Doxy.me.

C3f. Statistical Methods

Specific Aim 1: To determine the impact of cocaine dependence and oxytocin on functional connectivity between corticolimbic brain regions during acute social stress.

Hypothesis 1A: The HC-PBO group will exhibit greater functional connectivity between the amygdala and prefrontal cortical regions (orbitofrontal and anterior cingulate cortices) than the CD-PBO group.

Hypothesis 1B: The CD-OT group will exhibit greater functional connectivity between the amygdala and prefrontal cortical regions (orbitofrontal and anterior cingulate cortices) than the CD-PBO group.

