Preprocessing: Post-acquisition preprocessing and statistical analysis of all of the neuroimaging data will be performed using FEAT (FMRI Expert Analysis Tool) Version 5.98, part of FSL (FMRIB's Software Library, www.fmrib.ox.ac.uk/fsl). Functional magnetic resonance imaging (fMRI) blood oxygen level dependent (BOLD) imaging data will be acquired using a standard multi-slice gradient echo planar imaging sequence (TR=2200 ms, TE=35 ms, 64 x 64 matrix, 3 mm isotropic voxels, 271 volumes). Data will be preprocessed using scripting tools from FMRI Expert Analysis Tool (FEAT) Version 5.98, part of FMRIB's Software Library (FSL; www.fmrib.ox.ac.uk/fsl). First non-brain signal will be removed using FSL's BET brain extraction. Scans will be corrected for motion using FSL's linear registration and scans will be spatially smoothed using a Gaussian kernel of 8 mm FWHM. Since head motion can impact functional connectivity analyses, participants with head motion exceeding 0.2 mm will be excluded from the analyses (Power et al., 2012). The "fsl_motion_correction" scripting tool will be used to identify and scrub motion artifacts from each participant's data (Power et al., 2013). Scans will be spatially co-registered with a standardized anatomical template (Montreal Neurological Institute) using a 12 parameter affine transformation (Rorden et al., 2000). **Analysis:** Functional connectivity will be measured using a PPI based approach (Friston et al., 1997). A customized square wave form representing the task (1 = stress condition and -1 = control condition) and the duration of each condition will be convolved with a double-gamma hemodynamic response function. A mask of the seed region will be made using a 12-mm diameter sphere located in the center of the left amygdala using the MNI coordinates (x, y, z = -22, 0, -22). The transformation parameters described above will also be applied to the mask. For each participant and each run of the MIST, the mean corrected and high pass filtered time series of the BOLD signal in the left amygdala will be extracted and used in a single subject whole brain PPI analysis. The PPI model will include (1) the task vector; (2) the time series of the BOLD signal in the left amygdala; (3) a term representing the positive task x seed interaction; and (4) a term representing the negative task x seed interaction. The first level analysis will generate contrast images of the parameter estimates for each of the four regressors. Since the hypotheses associated with Specific Aim 1 explore increases in amygdala - prefrontal cortical connectivity in response to social stress, the group analysis will focus on the positive interaction term. The contrast images of the parameter estimates of the positive interaction term will be entered into a 2nd-level random effects analysis. Unpaired t-tests will be used to test for the following group differences (Hypothesis 1A: CD-PBO vs. HC-PBO) and (Hypothesis 1B: CD-OT vs. CD-PBO). Analyses will be conducted using FMRIBs Local Analysis of Mixed Effects (FLAME 1). Additional analyses comparing (HC-OT vs. CD-OT) will be conducted using an unpaired t-test and applying the appropriate corrections for multiple tests. We will also conduct an exploratory gender analysis between the CD and HC women in the four groups (Domes, Heinrichs, Glascher, et al., 2007; Domes et al., 2010; Potenza et al., 2012). We anticipate that 15-20% of the subjects in each group will be female (n=6/8 per group). We

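### The Aim 1 PPI model has no task-versus-rest regressor, so a group difference in activation can pass for, or hide, a group difference in connectivity

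*Combined protocol and SAP*

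**What the plan says.** The section on the Montreal Imaging Stress Task (MIST) describes three conditions per run: "participants will be exposed to 40-second blocks of three different conditions (rest, control, and stress").

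C3f Statistical Methods, Specific Aim 1, codes only two of them: "A customized square wave form representing the task (1 = stress condition and -1 = control condition"). Rest is given no code. The seed is a filtered series, with no cutoff stated: "the mean corrected and high pass filtered time series of the BOLD signal in the left amygdala will be extracted".

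The model is then listed term by term: "The PPI model will include (1) the task vector; (2) the time series of the BOLD signal in the left amygdala", followed by ("3) a term representing the positive task x seed interaction; and (4) a term representing the negative task x seed interaction". The next sentence confirms that the list is complete: "The first level analysis will generate contrast images of the parameter estimates for each of the four regressors".

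One coefficient goes to the group level: "The contrast images of the parameter estimates of the positive interaction term will be entered into a 2nd-level random effects analysis". Hypothesis 1A predicts that the healthy controls on placebo (HC-PBO) show "greater functional connectivity between the amygdala and prefrontal cortical regions (orbitofrontal and anterior cingulate cortices) than the CD-PBO group". Hypothesis 1B predicts the same for the cocaine-dependent oxytocin group against the cocaine-dependent (CD) placebo group.

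The stress-minus-control activation analysis later in the same section is a separate secondary model. Nothing in the plan says that rest volumes are dropped.

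**The concern.** A PPI coefficient measures connectivity only if the model has already accounted for how the target responds to the task. With three conditions, two task regressors are needed to describe that response. The plan has one, stress minus control, so the target's response to stress and control jointly against rest is left unmodelled, and the interaction term can pick it up.

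The pilot in section C2c bears directly on 1A. It reports greater stress-minus-control activity in the left amygdala, which is the planned seed, in CD than in HC participants. It also reports greater control-minus-rest activity in the anterior cingulate (ACC), a named 1A target, in HC than in CD. With a positive target response, the first difference raises the CD coefficient and works against 1A, while the second raises the HC coefficient and works towards it. A significant or null 1A result in the ACC could therefore not be cleanly attributed to connectivity.

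1B is exposed only if oxytocin changes the amygdala's stress-minus-control response or the target's task response in the MIST. The plan states neither.

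The wording of terms 3 and 4 is a separate and smaller fault.

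**Working it through.** **The plan's own figure.** Power and Sample Size gives a difference of 3.6 and an RMSE of 4.0, so d = 3.6/4.0 = 0.9. At two-sided 0.05 with 40 per group, power is 97.8%; 80% power needs 21 per group. The stated pairing of 40 per group with 80% power is not reproduced, but the present point does not depend on it.

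**Algebra.** Let S and C be the stress and control indicators, with rest coded 0 (assumed). Let the seed be x = aS·S + aC·C − m + e, where m is the mean removed. Ignoring haemodynamic smoothing, S² = S, C² = C and SC = 0, so

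(S − C)·x = [(aS + aC)/2 − m](S − C) + [(aS − aC)/2](S + C) + (S − C)e.

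The task vector removes the first part. Nothing in the model removes the second. Bias therefore needs both aS ≠ aC and a target response g to S + C.

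**Hand approximation.** Two thirds of volumes are task, so the variance of S + C is (2/3)(1/3) = 2/9. With noise variance 1 and δ = aS − aC,

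bias ≈ g(δ/2)(2/9) / [(δ/2)²(2/9) + 2/3].

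- δ = 0.5, g = 0.5: 0.0278/0.6806 = 0.041 (simulated with a double-gamma response: 0.042).
- δ = 1, g = 1: 0.1111/0.7222 = 0.154 (simulated: 0.148).

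With S + C in the model, the simulated coefficient was 0.001 in both cases, against a true value of 0.

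**Group test.** All amplitudes are assumed. Settings: no true group difference, 40 per group, three 6-minute runs of nine 40-s blocks, TR 2.5 s, white noise SD 1, coupling 0.3, amplitude SD 0.2, one target, two-sided 0.05, 1000 trials per cell. SD is the between-person SD of the true interaction. False-positive rates for the planned model without filtering:

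| Case | Seed stress−control, HC/CD | Target task response, HC/CD | SD 0 | SD 0.1 | SD 0.2 | SD 0.3 |
|---|---|---|---|---|---|---|
| A | 0.1/0.5 | 0.4/0.4 | 51% | 18% | 7% | 6% |
| B | 0.1/0.5 | −0.4/−0.4 | 50% | 17% | 9% | 7% |
| C | 0.4/0.4 | 0.5/0.2 | 34% | 12% | 8% | 6% |
| D | 0.2/0.4 | 0.4/0.2 | 4% | 4% | 4% | 5% |
| E | 0.1/0.5 | 0.4/0.3 | 28% | 12% | 6% | 5% |
| F | 0.3/0.4 | 0.6/0.2 | 24% | 10% | 7% | 5% |
| G | 0.2/0.5 | −0.1/−0.4 | 61% | 21% | 10% | 7% |

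D to F follow the pilot directions with a positive target response. B and G assume target deactivation, which the documents do not report. Monte Carlo error around 5% is about 3.6% to 6.4%.

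- Largest spurious d without filtering: about 0.5, 0.27, 0.15 and 0.10 at SD 0, 0.1, 0.2 and 0.3.
- Direction of the coefficient difference (HC minus CD): −0.020 in E, 0 in D, +0.019 in F.
- Masking: in E the spurious d is −0.32, −0.17 and −0.08 at SD 0, 0.1 and 0.2. Against a true d of 0.9, power falls from 97.8% to 73%, 90% and 95%.
- Filtering: the task cycle is 3 × 40 = 120 s. A soft 100-s high-pass filter leaves rates up to 38% (G, SD 0); a sharp one gives 4% to 6% throughout.
- With S + C added: 3.4% to 6.7% in all 96 cells.

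**Larger amplitudes** (200 trials per cell, TR 2.2 s). With seed difference 1 in CD and 0 in HC, and target response 1 in both, false positives were 100%, 89% and 37% at SD 0.1, 0.2 and 0.4. The spurious difference of 0.148 at SD 0.1 is d ≈ 0.148/√(0.1² + 0.057²) = 1.29, taking 0.057 as the estimation error over three runs. Under a true d of 0.9, correct-direction power fell from about 98% to 0%, 12% and 65%. With S + C added, false positives were 4.5% to 5%.

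**On the plan's scale** (RMSE 4.0, 40 per group), a spurious 0.8, 1.6 or 2.5 beta units would give 14%, 42% or 79% rejections. A masking bias of 1.06 units would cut power from 98% to 80%.

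**Terms 3 and 4.** If term 4 is −1 times term 3, the intercept plus the four regressors make five columns of rank 4.

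**The case against.** The strongest reply is that no determinate harm is shown. Several parts of it stand:

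- The pilot ACC difference is for control minus rest. Stress minus rest is not reported, so a group difference in the joint task response is an inference.
- No activation difference is reported for the orbitofrontal cortex, the region used for sizing.
- In the pilot-direction cases (D to F), rates are 4% to 12% at SD 0.1 and 4% to 7% at SD 0.2. The highest rates in the table need no between-person variation in the true interaction, which is unlikely in a random-effects setting.
- Every rate depends on chosen amplitudes. The plan's RMSE of 4.0 is the total spread of the estimated coefficient; the documents do not split it into true variation and error, or give the activation scale.
- The planned whole-brain, cluster-corrected test was not simulated.

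These points limit what can be said about size. They do not supply the missing regressor, and the dependence on amplitude runs both ways: larger values make the problem much worse. Filtering is no defence while the cutoff is unstated.

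Terms 3 and 4 might also mean stress-by-seed and control-by-seed. That reading removes the redundancy but not the omission: with aS = aC = 0.5 and target response 1, the reported term was biased by about −0.16.

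**Conclusion.** The concern holds. The model as listed can give a biased interaction coefficient, and 1A rests on a group difference in it. 1B is exposed only conditionally.

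Neither size nor net direction can be derived from the documents. At the moderate amplitudes tabulated, the artefact stays below the planned d of 0.9 and is close to nominal at SD 0.2 or more (at most 10% false positives). At larger amplitudes it can exceed the planned effect. It vanishes when the two pilot differences offset each other or a sharp 100-s filter is used. These statements assume rest coded 0, a single +1/−1 interaction and a single-target test.

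The redundancy of terms 3 and 4 is a wording fault. Read as a duplicated regressor, or as two contrasts on one regressor, it does not bias the group t-test.

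This should be corrected, though the documents do not show that it would overturn a result.

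**What to change.** Specify the first-level PPI model as four regressors: stress minus control, stress plus control versus rest, the seed time series, and one (stress minus control) × seed interaction. Entering stress and control as two separate regressors against rest is equivalent for the first two. Test the positive and negative interaction as +1 and −1 contrasts on the single interaction regressor. State the code for rest and the high-pass cutoff.

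The cost is a change of SAP wording and refitted first-level models. It uses about one degree of freedom per 6-minute run, out of 360/2.5 = 144 volumes at the TR in MRI Data Acquisition, or 360/2.2 ≈ 164 at the TR under Preprocessing. No new data are needed.
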